9.6.4 Vital Signs

The analysis of vital signs data will include summary statistics for each vital sign parameter for baseline and each scheduled post-baseline assessment and/or changes from baseline over time. Unscheduled assessments will be excluded.

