8.2.3.1 Vital Signs

The following measurements must be performed: systolic/diastolic blood pressure, heart rate, respiratory rate, pulse oximetry, and temperature. The subject must be in a supine position in a rested and calm state for at least 5 minutes before blood pressure assessments are conducted. If the subject is unable to be in the supine position, the subject should be in most recumbent position as possible. The position selected for a subject should be the same that is used throughout the study and documented on the vital signs eCRF. The temperature location selected for a subject should be the same that is used throughout the vital signs eCRF. Record all measurements on the vital signs eCRF.

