9.4.2.3.4 Vital Signs

Summaries of vital signs data over time and/or changes from baseline over time will be provided.

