2.1 Objectives and Endpoints

Objectives	Endpoints		
Primary			
To evaluate the safety and tolerability of AMG 510 in adult subjects of Chinese descent with KRAS p.G12C-mutant advanced/metastatic solid tumors	Subject incidence of dose-limiting toxicity (DLT), treatment-emergent adverse events, treatment-related adverse events, and changes in vital signs, electrocardiograms (ECGs), and clinical laboratory tests		
To characterize the pharmacokinetics (PK) of AMG 510 in subjects of Chinese descent when administered orally (PO)	PK parameters of AMG 510 including, but not limited to, maximum observed plasma concentration (C _{max}), time to achieve C _{max} (t _{max}), and area under the plasma concentration time curve (AUC)		
Secondary			
To evaluate the preliminary efficacy of AMG 510 as a mono-therapy in subsets of solid tumors with the KRAS p.G12C mutation	Objective response, duration of response, progression-free survival (PFS), disease control, time to response (TTR), and duration of stable disease measured by computed tomography (CT) or magnetic resonance imaging (MRI) and assessed per Response Evaluation Criteria in Solid Tumors (RECIST) version 1.1 guidelines		

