9.6.3 Laboratory Test Results

The analyses of clinical laboratory test will include summary statistics over time and/or changes from baseline over time will be provided for each scheduled post-baseline assessments. Tables of maximum shift from baseline to the worst on-study value will be provided for selected laboratory values with NCI-CTCAE grade. The parameters in Appendix C will be summarized.

Subject incidence of suspected Hy's law cases (Hy's law predicts potential for drugrelated hepatotoxicity) will be summarized. A listing of alanine aminotransferase, aspartate aminotransferase, alkaline phosphatase, and total bilirubin values at each time point will be produced for the subjects suspected of Hy's law case.

Protocol Number: 20190147

Date: 17FEB2022 Page 22 of 28

Unscheduled assessments will be included in the shift tables.

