9.6.5 Physical Measurements

Physical measurement data will be listed and reviewed for each subject. Summaries of changes from baseline over time may be provided. Unscheduled assessments will be excluded from table summary.

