9.6.6 Electrocardiogram

Summaries over time and/or changes from baseline over time will be provided for all ECG parameters using central data. Subject's maximum change from baseline in QTcF will be categorized and the number and percentage of subjects in each group will be summarized. Subject's maximum post baseline values will also be categorized and the number of percentage of subjects will be summarized. Both scheduled and unscheduled assessments will be included in the determination of maximum change and value. All onstudy ECG data will be listed.

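### Vital signs measured off-schedule appear in no vital-sign output, because SAP 9.6.4 excludes them and plans no worst-value summary or listing

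*SAP*

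**What the plan says.** SAP 2.1 gives the primary safety endpoint as the subject incidence of DLTs, treatment-emergent events, "treatment-related adverse events, and changes in vital signs, electrocardiograms (ECGs), and clinical laboratory tests". Protocol 8.2.3.1 defines the vital signs to be measured as "systolic/diastolic blood pressure, heart rate, respiratory rate, pulse oximetry, and temperature" and has them recorded on a dedicated eCRF page.

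The whole analysis plan for these data is two short sections. Protocol 9.4.2.3.4 says "Summaries of vital signs data over time and/or changes from baseline over time will be provided". SAP 9.6.4 plans statistics at baseline and for "each scheduled post-baseline assessment and/or changes from baseline over time. Unscheduled assessments will be excluded". Neither section mentions a minimum, maximum, shift or categorical table, or a listing. SAP section 10 declares no departures from the protocol's analyses.

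The neighbouring SAP sections go further:
- 9.6.3 (laboratory): "Unscheduled assessments will be included in the shift tables", and those tables run to the worst on-study value.
- 9.6.6 (ECG): "Both scheduled and unscheduled assessments will be included in the determination of maximum change and value", and all on-study ECG data are listed.
- 9.6.5 (physical measurements): unscheduled values are left out of the table only, and "Physical measurement data will be listed and reviewed for each subject".

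**The concern.** Vital signs are the only one of these four domains with neither a worst-value output nor a listing. An off-schedule reading enters no mean, no range and no listing, so the report of this component of the primary endpoint cannot show it.

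This matters most for oxygen saturation. Protocol 2.3 names ILD/pneumonitis among the key risks to monitor, and Table 6-3 gives suspected cases a row of their own. From cycle 3 the Schedule of Activities sets clinic visits on day 1 of each 21-day cycle, so an acute change between visits would be measured, if at all, at an unscheduled contact. Protocol 6.2.1 also names changes in vital signs in its dose-cohort stopping rules, so the protocol treats them as relevant to decisions.

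**Working it through.** The plan states no figure on this point, so the check is mainly a comparison of texts, followed by a small illustration of scale.

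**Step 1. Follow an off-schedule reading through each planned output.**

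| Domain (SAP section) | By-visit summary | Worst-value output using unscheduled values | Listing |
|---|---|---|---|
| Laboratory (9.6.3) | scheduled assessments | yes, shift tables | liver tests in suspected Hy's law cases only |
| Vital signs (9.6.4) | scheduled only | none | none |
| Physical measurements (9.6.5) | optional, scheduled only | none | yes |
| ECG (9.6.6) | yes | yes, maximum value and maximum QTcF change | yes, all on-study data |

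Only the vital-signs row gives an unscheduled value nowhere to go.

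**Step 2. Check the route through adverse events.** Under Protocol Appendix 4, an abnormal vital sign is an adverse event if the investigator considers it clinically significant and not due to progression of the underlying disease. SAP 9.6.2 then tabulates it by system organ class and preferred term, with severity graded by CTCAE. The measured value and its change from baseline are not reported there.

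**Step 3. Check what happens at a scheduled visit.** SAP 9.1 includes ranges among the statistics for continuous data. Suppose one subject's reading falls by *d* points and the others do not change. The mean change moves by *d*/n: *d*/12 in a cohort of 12, *d*/6 in a cohort of 6. For an assumed *d* of 12 points, these are 1 and 2 points. The range does not dilute the reading in this way: its lower end shows the full 12-point fall if change is summarised, or the low reading itself if values are summarised (given that no other subject's is lower). Scheduled extremes therefore remain visible, and the gap is confined to unscheduled readings.

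**Step 4. Scale, by assumption.** Assume exactly one affected subject, measured only off-schedule. The planned vital-sign tables show 0 affected. A worst-value summary that uses all assessments would show:
- cohort of 12: 1/12 = 8.3%, exact 95% CI 0.2% to 38.5%;
- cohort of 6: 1/6 = 16.7%, exact 95% CI 0.4% to 64.1%.

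The intervals are Clopper-Pearson. For one event the lower limit is 1 − 0.975^(1/n), and the upper limit is the 97.5% point of a Beta(2, n − 1) distribution. The documents give no rate for such readings, so this shows how one case would be reported and does not predict how many would occur.

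**The case against.** A reader might infer that the signal vanishes from the primary safety endpoint altogether. The documents do not support that. The endpoint bullet also covers DLTs and adverse events, and a clinically significant fall in a symptomatic subject is the kind of reading that Appendix 4 turns into an adverse event. The Dose Level Review Team also sees vital signs (SAP 7.1.1), and the Medical Monitor may convene it at any time (Protocol 6.2.1). What stands against this is narrower. The adverse-event route depends on the investigator's judgement and does not report the value. The planned review meetings are tied to the first six subjects' 21-day window in each cohort. The sponsor also did not treat adverse-event reporting as a reason to drop the laboratory shift or QTcF tables.

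A reader might also infer that by-visit means hide a single large change. The planned ranges answer that for scheduled visits.

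Leaving unscheduled readings out of by-visit statistics is ordinary practice, and SAP 9.6.4 is consistent with Protocol 9.4.2.3.4. Both points are right. What is missing is a companion output of the kind that the other domains have. The general statement in SAP 9.1 that graphics may be presented commits to nothing for vital signs.

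Finally, a categorised table modelled on QTcF could not be programmed as the SAP stands, because 9.6.6 gives no cut-points and none exist for vital signs. That objection holds, and the fix below does not rely on such categories.

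**Conclusion.** The point holds, as a minor one. Under SAP 9.6.4 an unscheduled vital-sign value appears in no vital-sign output, although changes in vital signs are a named component of the primary safety endpoint and ILD/pneumonitis is a key risk. Such a value reaches the adverse-event tables only through the investigator's judgement, and then as a term and grade.

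The illustrated difference is 0 against one subject in 12 or in 6. It rests on one affected subject with no scheduled abnormal reading. The point also assumes that unscheduled readings are entered in the database, which the exclusion rule itself implies; the documents do not say how many to expect. The study is descriptive, so no hypothesis test, error rate or sample size changes.

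**What to change.** Keep the scheduled-only by-visit summaries in SAP 9.6.4 and add two outputs:

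1. For each subject and parameter, the worst post-baseline value and worst change from baseline, using scheduled and unscheduled assessments: the minimum for oxygen saturation, and both minimum and maximum for blood pressure, heart rate, respiratory rate and temperature. Summarise these descriptively by dose. If categories are wanted, specify the cut-points before database lock.
2. A listing of all on-study vital signs, with unscheduled assessments flagged.

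The cost is one table and one listing for at most 18 subjects, from data already on the vital-signs eCRF. The drawback is that subjects measured more often have more chances of an extreme value. The SAP already accepts this for its laboratory shift tables and ECG maxima, and flagging unscheduled readings in the listing lets a reader judge it.

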9.6.5 Physical Measurements

Physical measurement data will be listed and reviewed for each subject. Summaries of changes from baseline over time may be provided. Unscheduled assessments will be excluded from table summary.

9.6.6 Electrocardiogram

Summaries over time and/or changes from baseline over time will be provided for all ECG parameters using central data. Subject's maximum change from baseline in QTcF will be categorized and the number and percentage of subjects in each group will be summarized. Subject's maximum post baseline values will also be categorized and the number of percentage of subjects will be summarized. Both scheduled and unscheduled assessments will be included in the determination of maximum change and value. All onstudy ECG data will be listed.

9.6.7 Exposure to Investigational Product

Descriptive statistics of cumulative dose, number of cycles, duration of usage, number and percentage of subjects with dose modifications and reasons will be produced to describe the exposure to AMG 510. Subject-level data may be provided instead of the summary if the subject incidence is low or single dose is given.

9.6.8 Exposure to Concomitant Medication

The number and proportion of subjects receiving concomitant medication will be summarized by preferred term as coded by the World Health Organization Drug (WHO DRUG) dictionary.

9.7 Other Analyses

9.7.1 Analyses of Pharmacokinetic or Pharmacokinetic/Pharmacodynamic Endpoints

For AMG 510, PK parameters including, but not limited to C_{max} , t_{max} , and AUC will be determined from the concentration-time profile using standard non-compartmental approaches and considering the profile over the complete sampling interval. Based on

Protocol Number: 20190147

Date: 17FEB2022 Page 23 of 28

the review of the data, analyses to describe the relationship between AMG 510 exposure and either pharmacodynamic effect and/or clinical outcome may also be performed.

10. Changes From Protocol-specified Analyses

There are no changes to the protocol specified analyses.

11. Literature Citations / References

Clopper C.J. and Pearson E.S. The Use of Confidence or Fiducial Limits Illustrated in the Case of the Binomial. Bimetrika Vol. 26., No. 4 (Dec., 1934): 404-413

Kalbfleisch, J.D. and Prentice, R.L. The Statistical Analysis of Failure Time Data, New York: John Wiley & Sons; 1980

Klein, J.P. and Moeschberger, M.L. Survival Analysis: Techniques for Censored and Truncated Data, New York: Springer-Verlag; 1997

World Health Organization 2018 Statistics. Accessed at: http://www.who.int/en/news-room/fact-sheets/detail/cancer on 01 August 2019.

Protocol Number: 20190147

Date: 17FEB2022 Page 24 of 28

12. Prioritization of Analyses

No priority of output is planned for this study.

13. Data Not Covered by This Plan

The analysis of Biomarkers and PRO endpoint is not covered in this plan.

Date: 17FEB2022 Page 25 of 28

14. Appendices

Appendix A. BOR Calculation Algorithm

BOR by investigator (used in interim analysis) will need to be derived based on Timepoint response collected on RECIST 1.1 CRF. Table 14-1 provides the BOR determination per RECIST 1.1 for trials where response confirmation is required. A BOR determined by Table 14-1 is considered a *Confirmed_BOR*.

At interim analysis, an unconfirmed response rate may be reported in addition to the confirmed response rate. The unconfirmed rate includes subjects who achieved a PR or CR and are awaiting a confirmative scan (ie, unconfirmed responders). If these subjects have disease progression or death before the confirmative scan, then they are no longer considered as unconfirmed responder awaiting confirmative scan.

Table 14-1. BOR per RECIST 1.1

Criterion	Timepoint T1 Response	T1 ≥ 35 days after Baseline?	Timepoint T2 Response	T2 ≥ 35 days after Baseline?	T2 ≥ 28 days after T1?	BOR
C1	CR	Yes	CR	-	Yes	CR
C2			CR	-	No	SD
C3			PR, SD	-	-	Query data*
C4			PD	-	-	SD
C5			NE, No further	evaluations		SD
C6		No	CR	-	Yes	CR
C7			CR	Yes	No	SD
C8			PR, SD	-	-	Query data*
C9			PD	-	-	PD
C10			NE, No further	evaluations		NE
C11	PR	Yes	CR, PR	-	Yes	PR
C12			CR, PR	-	No	SD
C13			SD	-	-	SD
C14			PD	-	-	SD
C15			NE, No further	evaluations		SD
C16		No	CR, PR	-	Yes	PR
C17			CR, PR	Yes	No	SD
C18			SD	Yes	-	SD

Protocol Number: 20190147

Date: 17FEB2022 Page 26 of 28

C19			PD	-	-	PD
C20			NE, No further	evaluations		NE
C21	SD	Yes	CR, PR, SD, PD, NE, no more evaluation			SD
C22		No	CR, PR, SD	Yes	-	SD
C23			CR, PR, SD	No	-	NE
C24			PD	-	-	PD
C25			NE, No further	evaluations		NE
C26	PD		-			PD
C27	NE	-	NE, No further	evaluations		NE
C28		-	CR, PR, SD	Yes	-	SD
C29		-	CR, PR, SD	No	-	NE
C30		-	PD	-	-	PD

CR = complete response, PR = partial response, SD = stable disease, PD = progressive disease, and NE = not evaluable.

^{*}If a CR is truly met at first time point, then any disease seen at a subsequent time point, even disease meeting PR criteria relative to baseline, makes the disease PD at that point (since disease must have reappeared after CR). Best response would depend on whether minimum duration for SD was met. However, sometimes 'CR' may be claimed when subsequent scans suggest small lesions were likely still present and in fact the patient had PR, not CR at the first time point. Under these circumstances, the original CR should be changed to PR and the best response is PR.

Protocol Number: 20190147

Date: 17FEB2022 Page 27 of 28

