8.2.2 Efficacy Assessments

Radiological Imaging Assessment

The extent of disease will be evaluated by contrast-enhanced MRI/computed tomography (CT) according to RECIST version 1.1 (Section 11.8). All radiological imaging will be performed as indicated in the Site Imaging Manual provided by the

central imaging core laboratory. In order to reduce radiation exposure for subjects, low-dose CT should be utilized whenever possible.

The screening scans must be performed within 28 days prior to enrollment and will be used as baseline. All subsequent scans will be performed in the same manner as at screening, with the same contrast, preferably on the same scanner. Radiological assessment must include MRI/CT of the chest, abdomen and pelvis, as well as assessment of all other known sites of disease as detailed within the Site Imaging Manual (refer to separate Brain MRI section for details regarding MRI of the brain).

The same imaging modality, MRI field strength and IV and oral contrast agents should be used at screening should be used for all subsequent assessments. Liver specific MRI contrast agents should not be used. To reduce potential safety concerns, macrocyclic gadolinium contrast agents are recommended per National Health Institute guidelines or follow local standards if more rigorous.

During treatment and follow-up radiological imaging of the chest, abdomen, pelvis, as well as all other known sites of disease, will be performed independent of treatment cycle every 6 ± 1 weeks for the first 4 response assessments, with the first post-baseline scan to occur 6 ± 1 weeks after cycle 1 day 1. After four 6-week response assessments, radiological imaging and tumor assessment will be performed every 12 ± 1 weeks. Radiologic imaging and tumor assessment will be performed until disease progression, start of new anticancer treatment, death, withdrawal of consent or until end of study. Imaging may also be performed earlier/more frequently if clinically necessitated at the discretion of the managing physician. Radiographic response (complete response [CR], PR) requires confirmation by a repeat scan at least 4 weeks after the first documentation of response and may be delayed until the next scheduled scan to avoid unnecessary procedures. The minimum time interval for determination of stable disease is ≥ 5 weeks.

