11.8 Appendix 8. Response Evaluation Criteria in Solid Tumors Version 1.1 (RECIST v1.1)

Quick Reference

Definitions

- Measurable Lesions
 - Measurable Tumor Lesions Non-nodal lesions with clear borders that can be accurately measured in at least 1 dimension with longest diameter ≥ 10 mm in computed tomography/magnetic resonance imaging (CT/MRI) scan with slice thickness no greater than 5 mm. When slice thickness is greater than 5 mm, the minimum size of measurable lesion should be twice the slice thickness.
 - Nodal Lesions Lymph nodes are to be considered pathologically enlarged and measurable, a lymph node must be ≥ 15 mm in short axis when assessed by CT/MRI (scan slice thickness recommended to be no greater than 5 mm). At baseline and in follow-up, only the short axis will be measured and followed.
 - Nodal size is normally reported as 2 dimensions in the axial plane. The smaller of these measures is the short axis (perpendicular to the longest axis).
 - Irradiated Lesions Tumor lesions situated in a previously irradiated area, or in an area subjected to other loco-regional therapy, are not measurable unless there has been demonstrated progression in the lesion prior to enrollment.
- Non-measurable Lesions
 - All other lesions, including small lesions (longest diameter < 10 mm or pathological lymph nodes with ≥ 10 mm but to < 15 mm short axis with CT scan slice thickness no greater than 5 mm) are considered non-measurable and characterized as non-target lesions.
 - Other examples of non-measurable lesions include:
 - Lesions with prior local treatment: tumor lesions situated in a previously irradiated area, or an area subject to other loco-regional therapy, should not be considered measurable unless there has been demonstrated progression in the lesion.
 - Biopsied lesions
 - Categorially, clusters of small lesions, bone lesions, inflammatory breast disease, and leptomeningeal disease are non-measurable.

Methods of Measurement

- Measurement of Lesions The longest diameter of selected lesions should be measured in the plane in which the images were acquired (axial plane). All measurements should be taken and recorded in metric notation. All baseline evaluations should be performed as closely as possible to the beginning of treatment and not more than 4 weeks before study Day 1.

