Not all evaluated	No	NE
Unequivocal PD	Yes or No	PD
Any	Yes	PD

CR = complete response; PD = progressive disease.

^a "Non-CR/non-PD" is preferred over "SD" for non-target disease since SD is increasingly used as endpoint for assessment of efficacy in some trials, so to assign this category when no lesions can be measured is not advised.

Overall Response: Confirmation of Complete Response (CR) and Partial Response (PR) required

Overall Response First Time Point	Overall Response Second Time Point	Best Overall Response
CR	CR	CR
CR	PR	SD, PD or PRª
CR	SD	SD provided minimum criteria for SD duration met, otherwise, PD
CR	PD	SD provided minimum criteria for SD duration met, otherwise, PD
CR	NE	SD provided minimum criteria for SD duration met, otherwise, NE
PR	CR	PR
PR	PR	PR
PR	SD	SD
PR	PD	SD provided minimum criteria for SD duration met, otherwise, PD
PR	NE	SD provided minimum criteria for SD duration met, otherwise, NE
NE	NE	NE

CR = complete response; PD = progressive disease; PR = partial response; NE = not evaluable; SD = stable disease.

^a If a CR is truly met at first time point, then any disease at a subsequent time point, even disease meeting PR criteria relative to baseline, makes the disease PD at that point (since disease must have reappeared after CR). Best response would depend on whether minimum duration for SD was met. However, sometimes "CR" may be claimed when subsequent scans suggest small lesions were likely still present and in fact that subject had PR, not CR at the first time point. Under these circumstances, the original CR should be changed to PR and the best response is PR.

Special Notes on Response Assessment

- Nodal lesions Lymph nodes identified as target lesions should always have the actual short axis measurement recorded, even if the nodes regress to below 10 mm on study. In order to qualify for complete response (CR), each node must achieve a short axis < 10 mm, NOT total disappearance. Nodal target lesion short axis measurements are added together with target lesion' longest diameter measurements to create the sum of target lesion diameters for a particular assessment (timepoint).

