4.2 Subgroups

Subgroup analyses for selected secondary endpoints (ORR and PFS) may be performed by cancer type (NSCLC, Colon cancer and Pancreatic cancer).

5. Definitions

AUC:

The area under the plasma drug concentration-time curve (AUC) reflects the actual body exposure to drug after administration of a dose of the drug.

Baseline:

For any variable, unless otherwise specified the baseline is the last non-missing assessment taken prior to the first administration of AMG 510 treatment. Where baseline measurements are taken on the same day as AMG 510 and no times are present, it will be assumed that these measurements are taken prior to the study specified treatment being administered.

Protocol Number: 20190147

Date: 17FEB2022 Page 10 of 28

Baseline ECG Values in Triplicate:

The mean of the three triplicate ECG results should be calculated for baseline. If fewer than three triplicate ECG results are available, the mean of available triplicate should be calculated. For all post-baseline ECG, the mean of one triplicate ECG results at the same assessment will be calculated and used in the analysis. When an ECG is missing within a triplicate, all available data will be averaged for that time point.

Best Overall Response (BOR):

The best overall response for a subject is the best observed disease response per RECIST v1.1.

BOR is defined as the best response in the following order: CR, PR, SD, PD, or NE, where CR and PR require confirmation by a repeat, consecutive scan at least 4 weeks after the first documentation of response. A BOR of SD requires an on-study imaging of SD or better no earlier than 5 weeks after cycle 1 day 1, otherwise the BOR will be not evaluable (NE). Please see the details in Protocol Appendix 8 and refer Appendix A for deriving BOR calculation algorithm.

Change from Baseline:

Change from Baseline is the arithmetic difference between post-dose assessment and Baseline value.

Change (absolute) from Baseline = (Post-baseline Value - Baseline Value)

Percent Change from Baseline = [(Post-baseline Value-Baseline Value) / Baseline Value] ×100

Diseases Control Rate (DCR):

Diseases Control Rate is defined as the proportion of subjects in whom the best overall response is determined as CR, PR, or SD.

DLT:

A DLT is defined as any adverse event meeting the criteria listed in Protocol Section 6.2.2 occurring during the first treatment cycle of AMG 510 (day 1 through day 21) where a relationship to AMG 510 cannot be ruled out.

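### SAP Table 14-1 counts the 35-day minimum for stable disease from the baseline scan, whereas SAP Section 5 counts it from cycle 1 day 1, so an early scan can be scored as SD and can only raise DCR

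*SAP*

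**What the plan says.** SAP Section 5, under Best Overall Response, states: "A BOR of SD requires an on-study imaging of SD or better no earlier than 5 weeks after cycle 1 day 1". If that condition fails, BOR is NE. The same entry sends the reader to Protocol Appendix 8 for details and to SAP Appendix A for the derivation.

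In Appendix A, Table 14-1 has two timing columns for the minimum, one per timepoint. The first is headed "T1 ≥ 35 days after Baseline"; the second applies the same test to T2.

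Baseline is not C1D1. SAP Section 5 says that, unless otherwise specified, "the baseline is the last non-missing assessment taken prior to the first administration of AMG 510 treatment". For imaging, Protocol 8.2.2 says: "The screening scans must be performed within 28 days prior to enrollment and will be used as baseline". Protocol Appendix 8 limits the lead of baseline evaluations to "not more than 4 weeks before study Day 1".

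The protocol's own minimum (8.2.2) gives a length without a starting point: "The minimum time interval for determination of stable disease is ≥ 5 weeks". Start of treatment is, however, the origin for duration of stable disease in both Protocol Appendix 8 and SAP Section 5.

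**The concern.** The definition and the algorithm that implements it agree on the length of the minimum but start the clock at different dates. A programmer who codes Table 14-1 literally will assign SD to some subjects whom Section 5 excludes. The discrepancy runs one way, because the baseline scan never comes after first dose and the table's test is therefore never the stricter one.

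The subjects at risk are those scanned early because they were deteriorating, or because they stopped treatment early for a reason other than progression. Scoring a brief SD before progression as disease control is what a minimum interval is meant to prevent. BOR of SD feeds DCR and defines who enters the DoSD analysis; both are secondary, descriptive endpoints.

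**Working it through.** **Length.** 5 weeks × 7 = 35 days, so the two rules agree on length and differ only in anchor.

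**Size of the difference.** Let g be the number of days from the baseline scan to C1D1, from 0 to 28 (Protocol 8.2.2 and Appendix 8). Table 14-1 is satisfied from day 35 − g after C1D1; Section 5 requires day 35.

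| Baseline lead g (days) | Earliest scan accepted by Table 14-1 (days after C1D1) | Required by Section 5 |
|---|---|---|
| 0 | 35 | 35 |
| 7 | 28 | 35 |
| 14 | 21 | 35 |
| 21 | 14 | 35 |
| 28 | 7 | 35 |

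**Which scans are exposed.** The first scheduled scan is 6 ± 1 weeks after C1D1, that is 35 to 49 days after it, and passes both tests for every g. Two kinds of scan can fall earlier: scans prompted by clinical need (Schedule of Activities footnote k; Protocol 8.2.2) and end-of-treatment scans (Protocol 8.1.3 and 8.2.2). Example of the second kind: last dose on study day 21 and a scan at the 14-day limit on day 35, which is 34 days after C1D1. Table 14-1 accepts it if g is at least 35 − 34 = 1.

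Imaging then continues until progression, new therapy, death, withdrawal or end of study. In this example the safety follow-up visit, which ends the study for the subject, falls at about 21 + 30 to 21 + 37 = days 51 to 58. That is after the first scheduled scan window (study days 36 to 50). So the result changes only if the scheduled scan shows PD, is not evaluable or is not done.

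**Effect on the table.** All 30 rows of Table 14-1 were coded and run under both anchors, with g from 0 to 28, T1 from 1 to 49 days after C1D1, T2 later (to day 84) or absent, and every response pair. Moving the anchor from Baseline to C1D1 gives 15 row-to-row transitions, starting from 13 distinct rows (C21 has three destinations). All 15 start from SD:

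- 3 to PD: C4→C9, C14→C19, C21→C24.
- 6 to NE: C5→C10, C15→C20, C21→C23, C21→C25, C22→C23, C28→C29.
- 6 to a combination with no table row: from C2 and C7 (CR then CR, less than 28 days apart), C12 and C17 (PR then CR or PR, less than 28 days apart), C13 and C18 (PR then SD). Section 5's fallback makes these NE.

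Nothing changes when T1 is at least 35 days after C1D1, or when T2 is CR, PR or SD at least 35 days after C1D1. No confirmed CR or PR changes.

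Worked case: baseline 28 days before C1D1, SD at 20 days after C1D1, then PD. The scan is 20 + 28 = 48 days after Baseline, so the table gives SD (C21). Counted from C1D1 it gives PD (C24), or NE (C25) if no further scan follows.

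**Effect on endpoints.** One reclassified subject moves DCR by 1/12 = 8.3 points at n = 12, or 1/6 = 16.7 points at n = 6, where listings may replace the interval. As an illustration, 9/12 = 75.0% (Clopper-Pearson 95% CI 42.8 to 94.5) becomes 10/12 = 83.3% (51.6 to 97.9). In the DoSD analysis an added subject with early progression or death can lower the curve; one censored before any event leaves the estimate unchanged. ORR, DOR and TTR rest on confirmed CR or PR, and PFS does not use BOR.

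**The case against.** The strongest reply is that this is a slip in a column heading. Section 5 is explicit and study-specific, duration of stable disease also starts at treatment start, and Table 14-1 is worded generically for trials that require confirmation. The study program, which we cannot see, may already use C1D1. Every scheduled scan passes both rules, cohorts have at most 12 subjects, no hypothesis is tested, and the affected endpoints are secondary. All of this stands and limits the severity. It does not remove the mismatch: neither passage is given precedence, and Section 5 itself hands the derivation to the table. Appendix A introduces the table for investigator BOR at interim analysis, so its use for central review is less explicit, but the main efficacy analyses use investigator assessment.

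Three stronger readings are tempting and not supported:

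- A reader might infer that some scan pairs have no defined BOR. Table 14-1 does lack rows for some pairs in which both scans are too early, but Section 5's NE fallback covers them. The rows are missing under either anchor, so they do not result from this mismatch.
- A reader might see a second contradiction, because Section 5 gives NE when the minimum is unmet while rows C9, C19 and C24 give PD, and Protocol Appendix 8 has entries such as "SD provided minimum criteria for SD duration met, otherwise, PD". Section 5 ranks PD above NE and defers to both appendices, so a later PD can be read as giving BOR of PD. The sentence could be clearer, but the conflict is not established.
- A reader might take the 15 transitions as 15 wrong rows or as a forecast of affected subjects. They start from 13 rows and count combinations on a grid of possible scan dates, not expected patients.

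**Conclusion.** The inconsistency is real and internal to the SAP. The Table 14-1 headings are the outlier: as written they can accept SD up to 28 days sooner than Section 5 allows, as early as 7 days after first dose.

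The bias has one direction, since DCR can be raised but not lowered, and the DoSD set can gain subjects who do not qualify. Reach is narrow. It takes an unscheduled or early end-of-treatment scan of SD or better, followed by early progression, death, new therapy, withdrawal, or a missed or not-evaluable scan. The conclusion assumes that the table is programmed literally and that the screening scan is the imaging baseline. The DCR shifts are illustrative counts, and the documents do not show that any subject will be affected. This is a low-severity correction that could usefully be made.

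**What to change.** Before database lock, change both timing headings in SAP Table 14-1 to *≥ 35 days after cycle 1 day 1*, and check that the BOR program uses the C1D1 date.

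Optional tidying in the same edit:

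- Add rows with BOR = NE where both timing columns are No: CR then CR less than 28 days apart; PR then CR or PR less than 28 days apart; and PR then SD. This matches row C23 and Section 5.
- Clarify in Section 5 that, when the minimum is not met, BOR is PD if progression follows and otherwise NE, in line with rows C9, C19 and C24 and Protocol Appendix 8.

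The cost is a small SAP edit and a program check, with no protocol amendment. Compared with the table as written, DCR may stay the same or fall.
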